With improved techniques of electrosurgery, several randomized trials - the gold standard of clinical research, were performed. A randomized double blind study (15) performed in 369 patients, showed that diathermy incision is superior compared to scalpel incision with reduced incision time, less blood loss and reduced early postoperative pain. The same advantages have been reported using advanced diathermy technology by Lee et al(16). The mechanism of these positive effects of cutting electrosurgery is that the skin is cut with an electrode delivering pure sinusoidal current, which allows tissue cleavage by rapid cell vaporization without damage to surrounding areas; this may explain the absence of tissue charring and the subsequent healing with minimal scarring (17).

Taking together, the recently published advantages of diathermy in the skin incision could be extremely useful in preventing complications and decreasing maternal morbidity associated with CD. However, there are no clinical trials comparing scalpel and diathermy in the population of pregnant patients undergoing CD. To perform such trials will have direct translational value. In situations of emergency cesarean sections, as an example, it will provide important information on which method will be fastest with the least amount of blood loss.

OBJECTIVE

The objective of this study is to compare scalpel vs. diathermy in abdominal wall incision, in pregnant patients undergoing repeat elective cesarean delivery.

HYPOTHESIS

We hypothesize that the abdominal wall incisions made by diathermy compared to scalpel during repeat cesarean delivery will have less incision time, as well as less blood loss. Further we hypothesize that the use of diathermy, compared with scalpel will not increase post-operative pain.

METHODS

- 1) This is a randomized prospective study in women undergoing elective repeat cesarean delivery or repeat unplanned non-emergent cesarean delivery at Medical Center Hospital in Odessa Texas.
- 2) After informed consent is obtained, women undergoing cesarean delivery will be randomized into two groups:

Group One

Will undergo diathermy to incise the entire abdominal wall, which includes skin, subcutaneous tissue, rectus muscle until the peritoneal cavity is visible.

Group Two

Scalpel will be used to achieve the same aims

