1. Postoperative pain

SELECTION OF PATIENTS

Inclusion Criteria -

1. Multiparous pregnant women 18 – 45 years.
2. Gestational ages 37 weeks to 41 weeks,
3. Undergoing repeat elective or repeat unplanned non-emergent cesarean deliveries.

Women with medical comorbidities like hypertension, diabetes complicating pregnancy, pregnant women with or without prenatal care, and multiple gestations will also be included.

Exclusion Criteria –

1. Informed consent can't be obtained in a manner that allows for no impression of undue influence/pressure or sufficient time for patient to consider participation.
2. Primary Cesarean deliveries – as these can bias the selection.
3. Skin conditions such as infections, psoriasis, and eczema.

RECRUITMENT PLAN

Patients from University Women's Health Centre (Texas Tech OBGYN clinic) and also from Medical Center Hospital, Odessa, Texas will be recruited. Potential participants will be identified by a member of the study team or clinic/hospital personnel caring for the patient. In the latter case, study personnel will be contacted to meet the patient after the patient has expressed an interest in learning more about participation. All the participants will have the study procedures, risks, benefits and alternatives explained by a member of the study team.

Once informed consent is obtained they will be randomized with 1:1 allocation by a computer generated randomization process. Since the annual rate of cesarean

Protocol version: 1.0

Page 5 of 11

deliveries in the above-mentioned centers ranges 150 to 175, we expect to enroll a total of 100 patients, and we will allocate 50 patients to each group. Assuming a significance level of 0.05 and a power of 80%, and observing that there is a single measurement and null attrition rate, we will be able to detect at least moderate effect sizes ($d=0.50$) when performing independent means comparisons.

RISKS:

Diathermy –

- A. Possibility of poor wound healing,
- B. There are concerns that large or excessive scars may form,
- C. Unanticipated burns on skin, subcutaneous tissues and other vital organs.

Scalpel –

- A. Injury to the major blood vessels.
- B. Injury to the vital organs.
- C. Excessive bleeding

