From the review of recent literature there are some concerns raised regarding the use of diathermy for skin incisions (10, 11, 12). However, we believe that the use of cutting diathermy, as described in our protocol, does not increase patient risk within the study group. First, there is a concern that diathermy, while making skin incisions, may increase the risk of wound complications, as well as delayed wound healing. However these studies differ from ours in a number of ways: A) Most studies claiming increase in risk examine midline abdominal incisions, and our study employs Pfannenstiel skin incision. B) In some studies it is unclear if pure cut mode was employed. The use of a blend mode will cause more lateral spread of current. This may increase the amount of tissue damage, thus promoting wound complications. Our study will employ diathermy only in pure cut mode in a standard setting as per surgeon's preference. A recent Cochrane review, which includes only randomized trials (the highest form of scientific inquiry), found no significant difference in wound complications between scalpel and diathermy (18).

Second, there has been a case report of a severe burn injury on patients back while utilizing diathermy during cesarean delivery (19). The purported mechanism for this burn was an interaction between diathermy and amniotic fluid (19). However in our study, cutting diathermy will be used only in incision of skin, subcutaneous fat and rectus fascia. This use precludes any interaction between diathermy and amniotic fluid.

ADVERSE EVENTS REPORTING:

Any event deemed as an Adverse Event that is possibly related or unexpected to the study will be assessed at each data gathering point and will be reported to the TTUHSC IRB as described in the IRB policies and procedure manual. Monitoring of adverse events will start on the day of surgery.

BENEFITS – There are no guarantees of any benefit to study participants. However, participants may have potential benefits of using electrosurgery which include reducing the amount of blood loss, dry and rapid separation of tissues. For surgeons, there is a reduced risk of accidental cut injuries.

DATA ANALYSIS :

Distributions of operative time, blood loss and post-operative pain will be tested for normal distribution. Student's T test or the non-parametric equivalent will be used to compare these outcomes between the study and control group. Significance level will be set at 0.05.

DATA MONITORING PLAN:

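### The primary comparisons are unadjusted and their sidedness is undeclared; prespecified adjustment would probably add power at 100 patients, by an amount the documents cannot confirm

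*Combined protocol and SAP*

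**What the plan says.** The Data Analysis section checks the distributions for normality and then applies a "T test or the non-parametric equivalent will be used to compare these outcomes between the study and control group". It adds: "Significance level will be set at 0.05". It names no covariate, adjusted estimate or sidedness. The Recruitment Plan describes 1:1 computer-generated randomization without stratification.

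The sample-size statement is in the Recruitment Plan: "we expect to enroll a total of 100 patients, and we will allocate 50 patients to each group". At a significance level of 0.05, 80% power and no attrition, it says "we will be able to detect at least moderate effect sizes ($d=0.50$) when performing independent means comparisons". No standard deviation or raw difference is given in seconds or grams.

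The Hypothesis section is directional for the two primary outcomes: diathermy incisions "will have less incision time, as well as less blood loss". It does not declare a one-sided test.

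The third inclusion criterion reads "Undergoing repeat elective or repeat unplanned non-emergent cesarean deliveries". Women with comorbidities and multiple gestations are also eligible. Methods item 3, by contrast, restricts enrolment to elective repeat cesareans. Methods item 4 standardizes the length and depth of the skin incision.

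**The concern.** The timed interval runs from the first cut to the peritoneum, through tissue that has been operated on before in every patient. It is plausible that time and blood loss over that path vary with tissue thickness, with the number of earlier cesareans and with the circumstances of the delivery. An unadjusted test leaves all of that variation in the error term. With 50 per arm and no stratification, chance imbalance in such factors is also possible.

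Two things are at stake. If the tests are two-sided, the trial has about 70% power where the plan says 80%. And a step that could narrow that gap at the same 100 patients is missing from the plan.

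**Working it through.** **Inputs from the protocol:** n = 50 per arm, d = 0.50, significance level 0.05, no attrition, two primary outcomes. **Not in the protocol:** sidedness (both computed) and the covariate–outcome R² (assumed, range shown).

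**1. The plan's own figure.** The noncentrality is d·√(n/2) = 0.50 × √25 = 2.5, with 98 degrees of freedom.

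- One-sided 0.05: Φ(2.5 − 1.645) = 80.4% (noncentral t: 79.9%). This reproduces the stated 80% with 50 per arm.
- Two-sided 0.05: Φ(2.5 − 1.960) = 70.5% (noncentral t: 69.7%). This does not reproduce it.
- Two-sided n for 80% power: 2 × (1.960 + 0.842)² / 0.50² = 62.8, so 63 per arm (t: 64), or 126 to 128 patients.
- Two-sided effect detectable with 80% power at 50 per arm: (1.960 + 0.842) × √(2/50) = 0.560 (t: 0.566).

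**2. Effect of adjustment, two-sided 0.05.** Covariates that explain a share R² of the outcome variance shrink the residual SD by √(1 − R²), so the noncentrality becomes 2.5/√(1 − R²). Three covariates leave 95 degrees of freedom. Estimating three slopes also inflates the variance of the treatment effect by about 1 + 3/(100 − 3 − 3) = 1.032.

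| R² (assumed) | Power, slope cost ignored | Power, slope cost included |
|---|---|---|
| 0 | 69.7% | 68.3% |
| 0.10 | 74.2% | 72.8% |
| 0.20 | 79.0% | 77.7% |
| 0.30 | 84.1% | 82.9% |

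- R² needed for 80%: 1 − (0.50/0.566)² = 0.22, or between 0.24 and 0.25 with the slope cost.
- Break-even against no adjustment: 1 − R² = 1/1.032, so R² is about 0.03.
- Loss if the covariates explain nothing: 69.7 − 68.3 = 1.4 points.

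**3. If alpha were split to 0.025 per primary outcome.** Unadjusted two-sided power is about 59%. The R² needed for 80% is 1 − (0.50/[(2.241 + 0.842) × 0.2])² = 0.34 (t: 0.36), before the slope cost.

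**4. If the tests are declared one-sided.** Adjustment still helps: about 83% at R² = 0.10 and 87% at 0.20, before the slope cost.

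**5. The scale matters.** The figures above assume normal errors. Simulation with lognormal outcomes (an assumption; 50 per arm, d = 0.50 and R² = 0.20 on the log scale, two-sided 0.05, 6,000 runs) gave the results below. Repeat runs agreed within about two points.

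| Log-scale SD | Planned rank test | Adjusted model, raw scale |
|---|---|---|
| 0.3 | 67% | 77% |
| 0.5 | 68% | 73% |
| 0.8 | 67% | 63% |
| 1.0 | 68% | 57% |

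An adjusted model on the log scale kept about 79%. With strong skew, a raw-scale linear model would be worse than the test the plan already has.

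**The case against.** The best defence is that nothing here is invalid. An unadjusted comparison in a randomized trial is unbiased, and adjustment is an efficiency option whose benefit cannot be established from the documents. That stands, and it limits the point to a cheap improvement.

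A reader might infer that strong predictors are available and would restore 80% power. The protocol does not support that. It names no predictor of either outcome and gives no R² or SD. Restriction to repeat cesareans and the standardized skin incision may lower what covariates can explain, although a ruled skin incision cannot equalize the distance to the peritoneum. That BMI is in the routine record is also an assumption. Prior cesarean history must be checked because primary cesareans are excluded, but eligibility needs only one earlier cesarean, not the count.

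A reader might also infer that the stated 80% is simply wrong. That depends on the test being two-sided, which is the usual reading of an unqualified 0.05 but is not stated. One-sided, the figure is right.

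Two further objections shape the remedy. First, operator training level may be settled after allocation: patients are randomized once they consent, and nothing says the surgeon is assigned before the arm is known. Adjusting for it could then introduce bias. Second, adjustment deals only with imbalance in the covariates modelled, in the form modelled. It also does nothing about two primary outcomes each tested at 0.05, where the family-wise error is 1 − 0.95² = 9.75% if they are independent.

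**Conclusion.** The point holds in a limited form. The plan is unadjusted and does not declare sidedness. At d = 0.50 with 50 per arm, power is about 70% two-sided (80% power at d of about 0.57) and about 80% one-sided.

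Prespecified adjustment raises power under either reading once R² exceeds about 0.03. Two-sided, it reaches 80% only if R² is about 0.22–0.25 or more, separately for incision time and for blood loss, or 0.34–0.36 and slightly above if alpha is split. At R² = 0.10 power is still only about 73–74%. These figures assume roughly normal errors on the modelled scale and d = 0.50 relative to the unadjusted SD on that scale. Whether the covariates are that prognostic cannot be settled from the protocol, so adjustment should not be presented as a certain route back to 80%. It is still worth making, because the loss if the assumption fails is about 1.4 points.

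**What to change.** 1. State whether the tests are one- or two-sided. If two-sided, restate the power at d = 0.50 as about 70%, with 80% power at d of about 0.57.
2. For each primary outcome, prespecify as the primary analysis a linear model on a scale suited to skewed data, for example log time and log blood loss, with a rule for zero values. The terms are arm plus covariates fixed before randomization: BMI, number of prior cesareans and, if both types are enrolled, elective versus unplanned status. The inclusion criterion and Methods item 3 must be reconciled on that last question.
3. Include operator training level only if the operator is assigned before the allocation is known.
4. Report the adjusted difference, or the ratio on a log scale, with its 95% CI. Keep the planned unadjusted test as a supporting analysis.
5. State that the R² behind any power claim for the adjusted analysis is assumed, and show the range.

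The cost is abstraction of two or three chart fields, a conditional model in place of a t test, and about 1.4 points of power if the covariates explain nothing. No additional patients are needed.

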- 3) Only patients undergoing elective repeat cesarean delivery will be enrolled, this will decrease the likelihood of introducing bias into the outcome measures, as well as it will make the population more uniform.
- 4) A standardized abdominal wall incision will be made with either diathermy in cut mode or scalpel. Diathermy will be set in a cut mode with standard setting as per surgeon's preference. All patients in the study will get standard skin incision in terms of length and depth which will be marked by a ruler.
- 5) Incision start and stop time will be recorded by a "timer". A digital wall clock in the OR will be used to establish time. The timer will instruct the surgeon to "cut". The timer will record the time. Once the surgeon reaches the abdominal peritoneum, they will announce "stop". The timers will record the time. The incision time will be the difference between the "cut" and "stop" times. These times will be recorded in units of seconds.

- 6) Along the incision depth the bleeding points will be mopped with sponge laps, no suction will be used and total blood loss will be calculated by weighing the laps.
- 7) Blood loss will be recorded as follows: A "used" lap sponge will weighed. A "fresh" lap sponge will be weighed. These weights will be recorded. Blood loss will be calculated as the differences in these two weights. These weights will be recorded in grams.
- 8) As per standard of care spinal or epidural anesthesia will be administered by certified registered nurse anesthetist (CRNA). Post-operative pain will be managed as follows: 1) 300 micrograms of Morphine sulfate will be injected through then spinal needle or epidural catheter at the beginning of the case. 2) 30 milligrams of Toradol will be injected IM, in the left thigh, at the conclusion of the case. 3) 10 mg hydrocodone/325mg acetaminophen 1-2 tablets, per oral, every 4-6 hours, PRN pain.
- 9) Post-operative pain will be measured by a Numeric Pain Rating Scale (see below) scored as 0= no pain, up to 10= worst possible pain. This score will be assessed daily by resident staff at 6:00 to 7:00 AM from post –op day 1 until hospital discharge.
- 10) As per standard MCH protocol, within one hour preoperatively, Ancef 2-3gms will be administered IV. If the patient is Penicillin allergic, she will receive either 900 milligrams of Clindamycin or 1gram of Vancomycin.

OUTCOMES-

Both groups will be assessed for

Primary outcomes:

1. Incision time
2. Blood loss

Secondary outcome:

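### Two unranked primary outcomes are each tested at 0.05 with no stated success rule: family-wise error is up to 9.75% (non-negative correlation) if either may be claimed, and joint power is unstated if both are required.

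*Combined protocol and SAP*

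**What the plan says.** - **Outcomes.** Two items, incision time and blood loss, stand under "Primary outcomes" with no ranking. Postoperative pain is the only secondary outcome.
- **Data Analysis.** Each outcome is compared between groups by a t test or its non-parametric counterpart, and "Significance level will be set at 0.05". No adjustment, alpha split or testing order is given here or elsewhere.
- **Hypothesis.** Diathermy incisions "during repeat cesarean delivery will have less incision time, as well as less blood loss". The Introduction gives as one purpose of such trials to learn "which method will be fastest with the least amount of blood loss". Both wordings join the two outcomes. Neither is a decision rule.
- **Recruitment Plan.** One generic calculation, "Assuming a significance level of 0.05 and a power of 80" per cent, with 50 patients per group and no attrition, is said to detect d = 0.50 "when performing independent means comparisons". Sidedness is not given.
- **Naming.** Methods item 5 defines the time measure ("The incision time will be the difference between the" two recorded times, from the start of cutting to reaching the peritoneum). Data Analysis uses another term: "Distributions of operative time, blood loss and post-operative pain will be tested for normal distribution".

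**The concern.** With two primary outcomes, a plan must say what counts as success. Without that, the choice between one and both can be made after the results are known.

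The two choices have different costs. If a significant result on either outcome is enough, two tests at 0.05 give more than a 5% chance of at least one false primary claim. If both are needed, the false-positive rate is safe, but the chance of success is below the power of a single test, and the protocol gives only the single-test figure. The protocol's Conclusion says the results may help decide which incision method to prefer, so one overall judgement may rest on these two tests.

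**Working it through.** **Inputs.** From the protocol: two primary outcomes, 0.05 for each test, 50 per arm, d = 0.50, 80% power, no attrition. Not in the protocol: the sidedness and the correlation (rho) between the two test statistics. Both sidednesses are shown, with rho from 0 to 0.8 and the limit at 1. Power figures assume normal data and t tests; the protocol also allows a non-parametric test, so read them as approximate.

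**Step 1. The plan's own figure.** Noncentrality = d × √(n/2) = 0.50 × √25 = 2.5, with 98 degrees of freedom.
- One-sided 0.05: normal approximation Φ(2.5 − 1.645) = 80.4%; noncentral t 79.9%. The stated 80% reproduces.
- Two-sided 0.05: Φ(2.5 − 1.960) = 70.5%; noncentral t 69.7%. The stated 80% does not reproduce. At this size and level, 80% needs d of about 0.57.

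**Step 2. If either primary may be claimed.** With independent tests, family-wise error = 1 − (1 − 0.05)² = 1 − 0.9025 = 9.75%. With correlation it is 1 − P(neither statistic passes its critical value) under a bivariate normal distribution:

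| rho | two-sided | one-sided |
|---|---|---|
| 0 | 9.75% | 9.75% |
| 0.3 | 9.5% | 9.3% |
| 0.5 | 9.1% | 8.8% |
| 0.8 | 7.8% | 7.5% |
| 1 | 5% | 5% |

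**Step 3. If both are required.** The chance of a false joint claim is at most 5%, so alpha is not inflated. Joint power with d = 0.50 on both outcomes, starting from the plan's 80% per test (one-sided):
- rho 0: 0.799 × 0.799 = 63.8%
- rho 0.5 (simulation, 200,000 trials per setting): 68.5%
- rho 0.8 (simulation): 72.7%

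If one effect is d = 0.80 (illustrative) and the other 0.50, joint power is 79.2% to 80.0%, because the smaller effect then decides the result.

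Two-sided, with d = 0.50 on both, joint power runs from 0.697 × 0.697 = 48.6% to 60.6%. That range combines two problems: the second primary outcome and the sidedness mismatch in Step 1.

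**Step 4. Cost of Holm.** The smaller p-value is tested at 0.025 and, if significant, the larger at 0.05.
- Power to show both, two-sided, d = 0.50 on both: 48.6% falls to 47.4% at rho 0, and 60.6% to 58.6% at rho 0.8. The loss is 1.2 to 2.0 points.
- Only one effect real (d = 0.50 and 0), power for the real one: 69.7% falls to about 59% two-sided, and 79.9% to about 70% one-sided. The loss is about 10 to 11 points.

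**The case against.** The strongest reply is that the protocol reads as a joint aim. The Hypothesis links the two outcomes, the Introduction speaks of speed together with low blood loss, and the Results section expects improvement on both. Nowhere is either outcome alone said to make the trial positive. On that reading there is no alpha inflation. This stands as a limit: a reader might infer that the trial's false-positive rate is inflated, but the documents support that only if either result may be claimed. It does not close the gap, because a hypothesis is not a success criterion and the joint power is then missing.

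A second reply is that these are two separate questions, named in advance, each entitled to its own 0.05. Whether that needs family-wise control is partly convention, and having only two fixed outcomes limits selective claiming. A plan may take that position, but this one does not state it.

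A third reply concerns size. The documents give no correlation, so any figure below 9.75% is an assumption; as the correlation approaches 1 the error approaches 5%. A range of 7.5% to 10% should not be read as a result: its low end needs a correlation of about 0.8 with one-sided tests, and its high end is the Bonferroni bound, above anything reached with non-negative correlation.

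Finally, a reader might infer from the term operative time that the analysis section omits the first primary outcome or means the whole operation. The documents do not support this. Only one time measure is defined, the three variables in Data Analysis match the three listed outcomes one for one, and the Results section ties the term to abdominal wall incisions. It is a naming inconsistency.

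**Conclusion.** The point holds as a missing decision rule, and the plan should be changed. Its consequence depends on the rule: an error rate above the stated 0.05 if either primary may be claimed, or an undisclosed joint power below 80% if both are required. The size of the first depends on the unknown correlation. The second is appreciable only if both effects are near d = 0.50.

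The two-sided joint power of 49% to 61% should not be put down to having two primaries. Much of that shortfall comes from the single-test power being about 70% rather than 80% when tests are two-sided. That is a separate error in the power statement and would exist with one primary outcome.

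**What to change.** Before analysis, add one of these rules to the Data Analysis section:

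1. **Either primary may be claimed.** Apply Holm to the two primary p-values at a family-wise 0.05. Set both costs in Step 4 beside this choice: the loss is small if both effects are real, and about 10 to 11 points if only one is.
2. **Both are required.** Keep 0.05 for each test and state the joint power with its assumed effects, correlation and sidedness. The cost is that a clear result on one outcome alone would not count as success.

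Separately, state the sidedness in the Recruitment Plan and make the power match it: about 80% at one-sided 0.05, or about 70% at two-sided 0.05 with a detectable d of about 0.57 at 80%.

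As a minor wording point, use incision time, as defined in Methods item 5, in Data Analysis and Results.

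All this takes a few sentences and no extra patients. The price is a lower stated power under Holm, a two-sided test or a both-required rule.
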